Chairside CAD/CAM restorations are generally delivered with adhesive resin cements. The cement may or not require pre-treatment of the tooth by etching or a bonding agent. This creates potential confusion for a clinician as to what the optimal material selection and treatment process should be. A new adhesive resin cement (Suglue 3/3M) is the latest generation of dual cured resin cements from 3M with the innovation to use different tooth pre-treatment options, self-etch, selective enamel etch, or total etch depending on the type of restoration. This simplifies the selection process for delivery of restorations by minimizing the amount of different materials required.

This investigation will be a longitudinal clinical trial to study the long-term clinical performance of a new adhesive resin cement for chairside CAD/CAM restorations. Lithium disilicate chairside CAD/CAM onlays (IPS emaxCAD/Ivoclar) will be adhesively bonded using a selective enamel etch technique with a new generation universal adhesive based on Scotchbond Universal Adhesive (3M) and a new generation resin adhesive cement based on RelyX Ultimate (3M). Full contour zirconia crowns (3M Chairside Zirconia/3M) will be cemented using a self-adhesive technique with the new generation adhesive cement. All restorations may be followed up to five years of service.

5 Specific Aims

The specific aims of this project are:

1. Evaluate the short-term post-operative sensitivity associated with a self-etching resin cement for adhesive luting of chairside zirconia crowns.
2. Evaluate the short-term post-operative sensitivity associated with the adhesive luting technique for ceramic onlays using a selective enamel etch technique and a universal adhesive and dual cure resin cement.
3. Evaluate the longitudinal clinical performance of lithium disilicate ceramic onlays and full contour zirconia crowns for up to five years of clinical service, for a minimum of 3 years. The onlays and crowns will be evaluated with FDI criteria (Hickel et al., 2007 and 2010) for esthetic properties include surface luster, surface staining, margin staining, color match and translucency; functional properties include anatomical form, material fracture, retention, margin adaptation, occlusal contour and wear, and proximal contact and contour; and biological properties include post-operative sensitivity, recurrence of caries, erosion, abfraction as well as gingival index, and plaque index.

6 Research Plan: Methods and Materials

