6.1 Subjects

The patient population will be selected from current patients under clinical treatment at the University of Michigan Dental Clinics. Patients need to volunteer for the study and must sign the informed consent. Patients will be over 18 years of age, of either gender, and of any ethnic background. Each patient should have at least one carious lesion or defective restoration to be restored on a maxillary or mandibular premolar or molar. Each lesion or defective restoration should exhibit sufficient size to extend at least one-half the intercuspal width of the tooth requiring an onlay or full crown restoration. The onlays may contain between one and three cusps on the selected tooth as long as an occlusal margin will be present. All teeth will test vital and be asymptomatic at the beginning of treatment. No more than two restorations will be placed per patient. If a patient presents with more than two acceptable teeth for the study, molar teeth will be included prior to premolar teeth. Exclusion criteria will include:

Devital or sensitive teeth

Teeth diagnosed with symptoms of incomplete tooth fracture

Teeth with prior endodontic treatment of any kind

Teeth with a history of direct or indirect pulp capping procedures

Subjects with uncontrolled bruxism or parafunctional habits

Subject has known allergies to any product used during this study

Subject will not be available for the study duration of 5 years

Subjects with significant untreated dental disease to include periodontitis and rampant caries

Pregnant or lactating women

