7.2 Clinical Evaluation

Two independent evaluators will examine all restorations in the study. Clinical evaluations will be made at baseline, six months, one year, two years and three years. If feasible, subjects will return for additional follow-up visits at four and five years. Evaluation criteria are based on FDI criteria (Hickel et al., 2007 and 2010) for esthetic properties include surface luster, surface staining, margin staining, color match and translucency; functional properties include anatomical form, material fracture, retention, margin adaptation, occlusal contour and wear, and proximal contact and contour; and biological properties include post-operative sensitivity, caries, gingival index, and plaque index (see Appendix for FDI criteria description). Disagreements in evaluations will be discussed between the evaluators and a consensus judgment will be reached and recorded for every criteria.

Intraoral digital color pictures at a 1:1.5 magnification will be taken to document pre-operative, cavity preparation, and post-operative conditions. Facial and occlusal views of the tooth will be documented for both the pre-operative and post-operative conditions.

A post-cementation quadrant digital scan will be made of each test restoration using the OmniCam. Digital files will be recorded at the baseline, 6 months, 1 year, 2 year and 3 year. Optionally also at 4- and 5-year recall visits. Bite-wing radiographs and periapical radiographs of each test tooth will be available preoperatively and at the three-year recall for routine, standard of care monitoring of the restorations.

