In case of occurrence of any Adverse Event or Adverse Device Effect the appropriate form provided by 3M has to be filled in by the investigator. In case of any near incident or any event that could lead or led to any medical hazard for the investigator (user) of the investigational device the Incident/Near Incident form provided by the sponsor has to be filled in by the investigator.

Any adverse reactions to the treatment provided as part of the study will be fully investigated and recorded on the Adverse Event/Adverse Device Effect form (See Appendix), including details of the appropriate clinical action taken. An adverse event is defined as any unintended adverse experience associated with the study materials or study procedures that results in an unplanned medical assessment or treatment or changes the risk to subjects.

Restoration Failures

If a crown or onlay fails during the term of the study, the investigator will provide complete information on the manner of the failure and the proposed resolution to the study contact person at 3M. Failures associated with the bonding agent, cement, crowns and onlays that may be expected in this study include:

- loosening or complete loss of the crown or onlay

- fracture and/or chipping of the crown or onlay
- surface roughening or discoloration of the crown or onlay

Upon a determination that the crown or onlay failure did not result from other identifiable causes, and with 3M's prior approval, the Institution will make arrangements to replace the crown or onlay or carry out appropriate alternative treatment (i.e. replacement with a fixed or removable partial denture) at 3M's expense. 3M will not be responsible for any expenses incurred without its prior approval. If a crown or onlay fails after the term of the study, 3M will not be responsible for any costs incurred in its repair or replacement. 3M will have no responsibility for any other treatment a patient may receive during the term of the study or after the study has ended.

Monitoring

Monitoring visits will take place at the study center. During these visits, questions on the study conduct will be discussed and the study documentation will be reviewed. The study monitor will check whether the Clinical Investigation Plan was followed and whether the investigational device was applied according to the Instructions for use. The monitor will verify if appropriate patient consent is available for each patient and that it was included before enrolment.

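### Study length is given both as five years and as a three-year minimum, the term governing failure reporting has no stated length, and nothing obtains the status of subjects who miss a year 4 or 5 recall

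*Combined protocol and SAP*

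**What the plan says.** The visible text describes the length of follow-up in several ways:

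- **Eligibility (Section 6.1, repeated on the enrollment form in the Appendix).** An exclusion criterion reads "Subject will not be available for the study duration of 5 years".
- **Introductory text before Section 5.** "All restorations may be followed up to five years of service".
- **Aim 3 (Section 5).** Performance is evaluated "for up to five years of clinical service, for a minimum of 3 years".
- **Visits (Section 7.2).** The firm schedule is "Clinical evaluations will be made at baseline, six months, one year, two years and three years". After that, "If feasible, subjects will return for additional follow-up visits at four and five years". Digital scans follow the same pattern: "Optionally also at 4- and 5-year recall visits".
- **Failures (Section 7.3, Restoration Failures).** "If a crown or onlay fails during the term of the study, the investigator will provide complete information" to the sponsor. On cost, "If a crown or onlay fails after the term of the study, 3M will not be responsible for any costs" of repair or replacement.

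Section 8 makes Kaplan-Meier survival to the end of each recall period the primary analysis, without comparisons. It plans two datasets. The second holds all subjects with baseline data and fills missing primary outcomes by LOCF.

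**The concern.** There are two linked problems.

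The first is the undefined term. Two obligations, reporting a failure and paying for its replacement, depend on a period that could end at three years or at five. For a restoration that fails in year four, the visible text does not settle whether either obligation applies.

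The second is ascertainment. If year 4 and 5 recalls take place, Section 8 will produce survival figures for them. Attendance at an optional visit may depend on the state of the restoration. Possible replacement at the sponsor's expense could draw patients with failures back, while treatment elsewhere could keep them away. Kaplan-Meier assumes that censoring is unrelated to failure. Section 7.3 obliges the investigator to report failures but gives no route for learning of one in a patient who does not return. In the LOCF dataset, a restoration intact at year three stays intact on paper if its later failure is never seen.

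**Working it through.** **Passages side by side.** Take a failure in year four.

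- If the term is the three-year minimum of Section 5 and the firm schedule of Section 7.2, the failure falls after the term. It is outside the Section 7.3 reporting duty and outside cost cover.
- If the term is the five-year duration of Section 6.1, it falls within the term. It is reportable without any recall visit, and replacement may be covered, subject to the sponsor's prior approval and the absence of another identifiable cause.

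Section 7.2 does not say who judges feasibility, by what criterion, or whether for the whole study or for each subject.

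**Size.** The plan states no figure to reproduce: it gives no expected survival, dropout rate or target precision. What follows is illustrative.

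From Section 6.3: 40 restorations per type.

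Assumed: 38 intact at year three (38/40 = 95.0%), 2 of these fail in years 4-5, and 36 remain intact. True five-year survival is 36/40 = 90.0%.

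Let rf and ri be the proportions of failed and intact restorations whose patients return. Non-attenders are censored at year three, and years 3-5 are treated as one interval.

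- Kaplan-Meier: 0.95 × [1 − 2·rf / (2·rf + 36·ri)]
- LOCF, with missing status carried forward as intact: (38 − 2·rf) / 40

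| rf / ri | Kaplan-Meier | LOCF |
|---|---|---|
| 60% / 60% | 0.95 × (1 − 1.2/22.8) = 90.0% | 36.8/40 = 92.0% |
| 70% / 50% | 0.95 × (1 − 1.4/19.4) = 88.1% | 36.6/40 = 91.5% |
| 50% / 70% | 0.95 × (1 − 1.0/26.2) = 91.4% | 37.0/40 = 92.5% |
| 100% / 50% | 0.95 × (1 − 2/20) = 85.5% | 36/40 = 90.0% |
| 0% / 50% | 0.95 × (1 − 0/18) = 95.0% | 38/40 = 95.0% |

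Three things follow:

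- Equal return leaves Kaplan-Meier unbiased.
- Unequal return moves it in either direction.
- LOCF is correct only when every failure is seen (rf = 100%). Otherwise it is too high, by 1/40 = 2.5 points for each missed failure.

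**The case against.** The strongest reply is that this is an ordinary three-year study with an optional extension. Screening for availability over the longest possible follow-up is sensible, and five-year availability is compatible with a three-year minimum. If feasibility is decided once for everyone, stopping at year three or four is administrative censoring, which Kaplan-Meier handles. Section 7.3 reporting does not depend on attending a visit. The primary analysis is descriptive and names no five-year time point.

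Much of this stands. A reader might infer that year 4-5 failures are in fact captured selectively. The documents do not establish that. It requires subject-level attendance that depends on restoration status, and Section 7.2 leaves both readings open. A reader might also infer that the eligibility rule contradicts the visit schedule. It does not; the two lengths are simply never reconciled. Nor can it be said that late adverse events are followed for less time, since adverse event reporting in Section 7.3 is not tied to the term of the study.

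The wide range also needs care. The 85.5% and 95.0% figures rest on extreme return rates that nothing in the documents supports. In the 85.5% case the LOCF dataset returns the assumed truth of 90.0%, so the downward error is confined to the Kaplan-Meier estimate that censors non-attenders.

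Finally, the consent pages were removed, Sections 6.2 and 12 contain redactions, and Section 6.4 shows no text. The term may be defined there, so the gap can be asserted only of the visible text.

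The reply does not answer one question: if a year 4 or 5 recall is held and some subjects do not attend, how is their status learned? No section says. A duty to report a failure does not help the investigator to discover it.

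**Conclusion.** The point holds in limited form. The visible documents carry a five-year study duration and a three-year minimum without reconciling them, and they hang failure reporting and replacement cover on a term with no stated length.

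The risk of bias is conditional. It arises only if year 4-5 recalls are held, attendance varies by subject, and attendance is related to failure. Kaplan-Meier survival can then be wrong in either direction. LOCF needs less: any missed failure inflates survival, whatever the reason it was missed. A single study-wide decision to stop creates no selection.

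The documents supply neither the size nor the direction. Under an assumed 90.0% true five-year survival, moderate differences in return shift Kaplan-Meier by about 1 to 2 points (88.1% to 91.4%). The span of 85.5% to 95.0% is an outer illustration, not an expected error. The scheduled visits to year three and the planned 40 + 40 restorations are unaffected. The change is worth making because it is cheap and protects the late survival estimates.

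**What to change.** 1. Define the term of the study once, and make the introductory text, Sections 5, 6.1, 7.2 and 7.3, and the enrollment form agree with it. The length itself is for the sponsor and investigator to settle.
2. State in Section 7.2 whether feasibility is decided for the study or for each subject, and by whom.
3. Whenever a year 4 or 5 recall is held, require a short telephone status check for every subject not seen: restoration in place, repaired, replaced or lost, with date; tooth treated or extracted.
4. Use the answers in the survival analysis and the failure records. In Section 8, censor subjects of unknown status at their last known status date instead of carrying intact status forward.

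**Cost.** At most 60 patients × 2 recalls = 120 short calls, one CRF page, and an amendment approved by the investigator, sponsor and IRB. Section 7.1 already uses telephone follow-up to limit recall loss, and Section 11 provides a full-time coordinator, although Section 7.1 does not say who makes the existing calls.

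**Downside.** Status by telephone is patient-reported, and FDI scores stay missing at those times.

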7.3 Data Management

Case Report Form (CRF)

For this study, all required data will be entered into the electronic CRFs (eCRFs), by the end of each day by [REDACTED], the Research Clinic Coordinator at the University of Michigan.

Approval is required by the principal investigator [name]. Up to 50 sets of paper copies of the CRFs may be provided to the site in the event that computer access is limited. If paper CRFs are used, they are the source data and must be entered into the eCRF by the end of each day. If study-related data are recorded for the first time directly into the eCRF, then the eCRF is the source document. Completed paper and eCRFs will be reviewed by the site monitor to ensure accuracy and consistency of subject data. Any discrepancies found during CRF review are to be clarified by the Investigator or designee.

In case paper format would need to be used the entries will be made with blue ball-point pen. In case of necessary corrections, the wrong entry will be crossed out and the new entry will be written beside it. No erasure is allowed for corrections. Changes or corrections will be dated and initialized by the investigator or assigned person(s). The documentation of each patient visit (baseline, follow-ups) must be signed and dated by the conducting investigator. If paper versions would be used the data would be directly entered into Clindex for electronic data capture by [REDACTED]

[REDACTED]

The completed CRFs and Adverse Events/Incident Reports will be retained together with the investigator's study file for a period of 10 years after completion of the study at the study center.

3M intends to use electronic data capture (eDC) software (Clindex) for this study. Sites will be trained on the eDC software prior to study enrollment. Each site will be provided with a manual, including instructions on how to complete the CRFs and how to make CRF corrections. Data may be recorded onto data collection sheets (provided by 3M) prior to data entry or may be entered directly into the eDC system. Once the forms are completed, the monitor will review the CRFs to assure accuracy and completeness. The Investigator must review and sign the CRFs for each subject in a timely fashion following completion.

Adverse Event / Adverse Device Effect Form – Incident/Near Incident form

In case of occurrence of any Adverse Event or Adverse Device Effect the appropriate form provided by 3M has to be filled in by the investigator. In case of any near incident or any event that could lead or led to any medical hazard for the investigator (user) of the investigational device the Incident/Near Incident form provided by the sponsor has to be filled in by the investigator.

Any adverse reactions to the treatment provided as part of the study will be fully investigated and recorded on the Adverse Event/Adverse Device Effect form (See Appendix), including details of the appropriate clinical action taken. An adverse event is defined as any unintended adverse experience associated with the study materials or study procedures that results in an unplanned medical assessment or treatment or changes the risk to subjects.

Restoration Failures

If a crown or onlay fails during the term of the study, the investigator will provide complete information on the manner of the failure and the proposed resolution to the study contact person at 3M. Failures associated with the bonding agent, cement, crowns and onlays that may be expected in this study include:

- loosening or complete loss of the crown or onlay

- fracture and/or chipping of the crown or onlay
- surface roughening or discoloration of the crown or onlay

Upon a determination that the crown or onlay failure did not result from other identifiable causes, and with 3M's prior approval, the Institution will make arrangements to replace the crown or onlay or carry out appropriate alternative treatment (i.e. replacement with a fixed or removable partial denture) at 3M's expense. 3M will not be responsible for any expenses incurred without its prior approval. If a crown or onlay fails after the term of the study, 3M will not be responsible for any costs incurred in its repair or replacement. 3M will have no responsibility for any other treatment a patient may receive during the term of the study or after the study has ended.

Monitoring

Monitoring visits will take place at the study center. During these visits, questions on the study conduct will be discussed and the study documentation will be reviewed. The study monitor will check whether the Clinical Investigation Plan was followed and whether the investigational device was applied according to the Instructions for use. The monitor will verify if appropriate patient consent is available for each patient and that it was included before enrolment.

Furthermore he/she will check the availability, completeness, logicalness, accuracy and legibility of certain study documents, the CRFs and the Adverse Event/Incident forms. The occurrence of any new Adverse Event/Adverse Device Effect/(near) incident will be reported in the monitoring report and copies of the forms will be collected. Certain data in the CRFs will be verified with source documents (patient files).

The study will be monitored at appropriate intervals by the study monitor, or his/her designee, by means of visits to the study site to evaluate study data and any photographs. Study monitoring visits will involve review of the study status and any issues pertaining to it. All Informed Consent forms, HIPAA forms will be reviewed for signatures; all CRF's will be reviewed for completeness of data entry and that the study protocol is being followed; the subjects'

profiles will be checked to ensure they meet the inclusion and exclusion criteria. Materials will be checked for adequate storage and sufficient quantity to meet the study needs.

Data collection and Data corrections

During monitoring, CRFs will be checked for accuracy, legibility, logicalness and completeness, that all patients have given informed consent, meet selection criteria, and have had treatments randomly allocate in accordance with the study protocol. Resulting changes in the data will be initialized and dated by the person who changed them. If all open questions could be cleared with the investigator, copies of the signed Adverse Event/Incident forms will be provided for the Study Monitor's file. Data entry will be done by [REDACTED], Research Clinic Coordinator of the Cariology, Restorative Sciences Clinical Research Unit.

8 Statistical Analysis

In general, all analyses will be conducted separately by type of restoration; onlay or crown. Means and standard deviations were calculated for all clinical measurements and assessments. Categorical variables were summarized in frequency distributions.

There will be two datasets analyzed at each recall period; (1) one dataset consisting of subjects who were enrolled up to and including that recall period, and (2) one dataset consisting of all subjects with baseline data. In the second dataset (2) primary and secondary outcome variables which are missing will be imputed using the method of last observation carried forward (LOCF), wherein the last observed values for that variable will be carried forward to all remaining timepoints.

The primary analysis for this study will be the percent of intact/surviving restorations from baseline to the end of each recall period. This will be estimated using the Kaplan-Meier method, there will be no direct comparisons within this analysis. The median survival time of a restoration will be presented alongside survival curves.

The secondary analyses for this study will relate to the FDI criteria for esthetic properties including surface luster, surface staining, margin staining, color match and translucency; functional properties including anatomical form, material fracture, retention,

margin adaptation, occlusal contour and wear, and proximal contact and contour; and biological properties including post-operative sensitivity, caries, gingival index, and plaque index (see Appendix for FDI criteria description). The FDI criteria will be assessed at each recall period versus their respective baseline scores for a particular restoration within a particular subject. FDI criteria which are measured in an ordinal-discrete manner will be assessed using the Wilcoxon-signed rank test. Criteria which are measured continuously such as PI and GI will be assessed using the student's t-test, in the event that the PI and GI scores do not appear to be Normally distributed this assessment will shift to be done using the Wilcoxon-signed rank test.

A two-sided alpha of 0.05 will be used for all comparisons. There will be no adjustments made for multiplicity.

All statistical analyses will be performed e.g. using SAS version 9.4 or above (SAS Institute, Cary, NC).

9 Project Time Line

The recruitment of patients and clinical placement of restorations will begin immediately upon approval and funding of the project. It is anticipated to take 9-12 months to recruit and place the restorations required for the study.

Protocol Amendments and Discontinuing the Study

After approval of the study protocol, any changes to the content of the study documentation must be described in an Amendment Form and be approved by the PI, 3M, and the reviewing IRB prior to implementation. Any decision as to whether to prematurely stop the study will be taken jointly by the PI, 3M, and the IRB. Where early termination of the study occurs, subjects will receive appropriate follow up dental treatment.

10 Equipment

A CEREC system including a CEREC OmniCam and PrimeScan, MCX mill, Programmat oven, and SpeedFire oven is available at the University of Michigan for use during the study. All other instrumentation required for placement and clinical evaluation of the restorations is available through the Research Clinic of the Department of Cariology, Restorative Sciences, and

Endodontics at the University of Michigan School of Dentistry. Additional measurement instrumentation to include measuring microscopes, scanning electron microscope, computer analysis, and intraoral imaging equipment is available within the School of Dentistry.

11 Facilities

The Graduate General Dentistry Clinic maintains a two chair Clinical Research Unit for clinical research within the department. A full time Clinical Research Coordinator is dedicated to the Clinical Research Unit as well. She will coordinate and schedule all patient appointments, maintain recall schedules, and collate data collected. A Certified Dental Assistant will also provide clinical support as well. Additional dental materials and instruments as well as personnel support will be provided by the Graduate General Dentistry Clinic as needed.

12 Additional Sponsorships:

No other sponsorships are presently available or will be applied to this project.

In the event that study restorations should fail and require replacement, patients may elect to have a laboratory-fabricated restoration placed instead of another test restoration. [REDACTED]

[REDACTED]

[REDACTED]

[REDACTED]

13 References

[figure not shown]
[figure not shown]
[figure not shown]
[figure not shown]
